## Transformations

*If you plan on transforming, centering, recoding the data, or will require a coding scheme for categorical variables, please describe that process.*

No transformations are planned. If needed, categorical variables will be dummy coded as n-1 predictors. Reference categories would be: Medication changes (no change), race/ethnicity (Caucasian/Non-Hispanic), ADHD presentation (Combined Presentation). All other categorical variables are dichotomous and therefore would not require dummy coding.

## Follow-up analyses

*If not specified previously, will you be conducting any confirmatory analyses to follow up on effects in your statistical model, such as subgroup analyses, pairwise or complex contrasts, or follow-up tests from interactions? Remember that any analyses not specified in this research plan must be noted as exploratory.*

Planned contrasts/post-hocs are described under the statistical model question above. Unless otherwise specified, significant main effects/interactions in the omnibus model will be followed by Bonferroni-corrected post hocs/contrasts to characterize the omnibus effects.

## Inference criteria

*What criteria will you use to make inferences? Please describe the information you'll use (e.g. specify the p-values, Bayes factors, specific model fit indices), as well as cut-off criterion, where appropriate. Will you be using one or two tailed tests for each of your analyses? If you are comparing multiple conditions or testing multiple hypotheses, will you account for this?*

P-values and Bayes Factors will be reported. P-values will be considered primary in cases of discrepant results (to follow current conventions in the field). P =.05 or lower and BF =3 or greater will indicate significant effects.

For the Bayes Factors, BF10 or BF01 will be reported based on which value is greater than 1 as recommended.

Post-hoc tests will be corrected using Bonferroni corrections for multiple comparisons. No corrections will be made for the omnibus tests. These omnibus tests already include 2 variables per outcome to minimize the number of tests.

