## Recommended elements

1. All hypothesized interactions are expected to look like Figure 1 in Redick (2015). In other words, no pre-treatment group differences, and differential improvements favoring the group hypothesized to improve. Should pre-treatment group differences be observed, differential improvements favoring the group hypothesized to improve would be observed when using post-treatment covaried for pre-treatment analysis (residualized gain scores). No differences in this test indicate equivalence between interventions.
2. P-values and Bayes Factors will be reported. P-values will be considered primary in cases of discrepant results (to follow current conventions in the field). P-values of .05 or less will be considered significant (after Bonferroni corrections for post-hoc tests). Bayes Factors of 3 or greater will be considered significant.

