## Sample size

*Describe the sample size of your study. How many units will be analyzed in the study? This could be the number of people, birds, classrooms, plots, interactions, or countries included. If the units are not individuals, then describe the size requirements for each unit. If you are using a clustered or multilevel design, how many units are you collecting at each level of the analysis?*

The final analyzed sample size is expected to be BPT = 27, CET = 27. BPT collection is complete; the last CET group is anticipated to be complete in May/June 2017.

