#### Covariates and Data Handling

1. To describe the samples, the BPT and CET samples will be compared at pre-treatment on gender, age, SES (Hollingshead scores), WASI-II/WISC-IV Verbal Comprehension Index IQ standard scores, medication status (no/yes), race/ethnicity (US Census categories), comorbidities (no/yes), teacher reported ADHD symptoms (BASC-2 attention problems and hyperactivity T-scores), parent reported ADHD symptoms (BASC-2 attention problems, hyperactivity T-scores, CSI-IV raw severity scores for attention problems and hyperactivity/impulsivity), parent reported ODD symptoms (CSI-IV raw severity scores). Variables showing significant between-group differences at  $p = .05$  or less, corrected for multiple comparisons, will be used as covariates in all above analyses (simultaneous entry). We decided to sacrifice power if needed to control for any pre-treatment differences.
2. The CET vs. BPT pre-treatment descriptive analyses will also be conducted for the treated vs. untreated samples. For the purposes of these analyses, the BPT and CET participants will be combined as the 'treated' sample, and those who declined or otherwise were offered but did not participate in BPT and CET will be combined as 'untreated.' We will not conduct treated vs. untreated analyses separately for the BPT and CET groups due to low n. The same significance

criteria and correction for multiple comparisons will apply as for BPT vs. CET.

3. All hypothesized interactions are expected to look like Figure 1 in Redick (2015). In other words, the expected interaction pattern would be due to no pre-treatment group differences, and differential improvements favoring the group hypothesized to improve.

Unless otherwise specified below, all omnibus tests will be 2 (group; between) x 2 (variable; within) x 2 time points (pre, post; within) mixed-model ANOVA or ANCOVA. ANOVA vs. ANCOVA decision will be based on whether there are significant  $p = .05$  (or lower) group differences on any pretreatment variables as detailed in previous section. Tests that specify independent-samples or paired-samples t-tests will be run as between-group and within-group ANCOVAs, respectively, if covariate adjustments are needed based on analysis of pretreatment characteristics described in previous section.

Analyses will be run using JASP 0.8.1 (or current version).

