#### Primary Outcome

1. Near-transfer: 2 group x 2 task x 2 time points (pre, post). Tasks are Rapport phonological (PH) and visuospatial (VS) working memory tests. Critical test is the group x time interaction. The 2 tasks are included in the omnibus ANOVA to (1) address recommendations to probe cognitive abilities using multiple tests, and (2) maximize power for the critical group x time interaction. The 2 working memory tests are considered to tap the same 'central executive' working memory; they differ in whether that central executive is processing phonological or visuospatial information. If the group x time interaction is significant at  $p = .05$  (or lower), it will be followed by Bonferroni-corrected within-group post-hocs for each task and ANCOVA of post-treatment covaried for pre-treatment separately for each task (i.e., residualized gain scores). These post-hocs will also be performed if the main effect of time is significant (but not the group x time interaction) to allow us to better characterize change within each group (i.e., did each treatment produce significant change?). Stimuli correct per trial will be used.

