#### Recommended elements

10. All hypothesized interactions are expected to look like Figure 1 in Redick (2015). In other words, no pre-treatment group differences, and differential improvements favoring the group hypothesized to improve. Should pre-treatment group differences be observed, differential improvements favoring the group hypothesized to improve would be observed when using post-treatment covaried for pre-treatment analysis (residualized gain scores). No differences in this test indicate equivalence between interventions.

11. P-values and Bayes Factors will be reported. P-values will be considered primary in cases of discrepant results (to follow current conventions in the field). P-values = .05 or lower will be considered significant (after Bonferroni corrections for post-hoc tests). Bayes Factors = 3 or greater will be considered significant.

no file selected

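### The Bayes factor threshold has no direction and the plan has no inconclusive category, so non-significant results can be read as equivalence when the data are merely weak

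*Combined protocol and SAP*

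**What the plan says.** The Bayes factor rule appears in three places. Inference criteria, in the Analysis Plan, states "P =.05 or lower and BF =3 or greater will indicate significant effects" and then "For the Bayes Factors, BF10 or BF01 will be reported based on which value is greater than 1 as recommended". Recommended elements appears twice. Item 2, after the hypotheses, says "Bayes Factors of 3 or greater will be considered significant"; item 11, in the Analysis Plan, says "Bayes Factors = 3 or greater will be considered significant". None of the three says whether the threshold applies to BF10, to BF01 or to both, or what BF01 of 3 or more means. All three make the p-value primary when the two measures disagree.

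Several parts of the plan rest on null conclusions:
- Research question 1 asks whether feasibility and acceptability are comparable between arms, and question 3 asks about non-inferiority.
- Items 6 and 7 of the outcomes predict no significant differences on the CSQ-8 and BTPS.
- Both Recommended elements lists (items 1 and 10) say that finding no difference in the post-treatment comparison adjusted for pre-treatment shows the interventions to be equivalent.

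No margin or equivalence test is given. Covariates and Data Handling names the software (JASP) but no prior scale.

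**The concern.** The reported value is whichever of BF10 and BF01 exceeds 1, that is, max(BF10, 1/BF10). A threshold of 3 on that value, with no direction attached, cannot separate evidence for an effect from evidence against one.

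What is at stake is the reading of non-significant results. A correctly directed BF01 is the only planned measure that could tell absence of a difference from too little data. The plan assigns BF01 no meaning and has no label for a result that favours neither side. With p-values primary and the equivalence sentence in place, a non-significant comparison can be reported as equivalence whatever the Bayes factor shows.

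**Working it through.** The plan gives no power, effect size, prior or error rate for this rule, so there is no figure of its own to reproduce.

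**Inputs from the plan.** Sample size: "The final analyzed sample size is expected to be BPT = 27, CET = 27". For the primary outcome: "Critical test is the group x time interaction". Averaged over the two tasks and without covariates, that interaction is a two-sample t-test on change scores. The CSQ-8 and BTPS comparisons are specified as independent-samples t-tests. Degrees of freedom: 27 + 27 − 2 = 52. Effective size: 27 × 27 / 54 = 13.5.

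**Assumptions.** A zero-centred Cauchy prior on the standardised difference, with scale r = 0.5, 0.707 or 1.0, and a true difference d of 0 or 0.5 SD.

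**Step 1: thresholds.** BF10(t) is the noncentral t density (52 df, noncentrality d√13.5) averaged over the prior, divided by the central t density. The equations BF10 = 3 and BF01 = 3 are solved for |t|.

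| r | Maximum BF01 (t = 0) | BF01 ≥ 3 needs | BF10 ≥ 3 needs |
|---|---|---|---|
| 0.5 | 2.79 | not attainable | abs(t) ≥ 2.41 |
| 0.707 | 3.65 | abs(t) ≤ 0.69 | abs(t) ≥ 2.44 |
| 1.0 | 4.91 | abs(t) ≤ 1.05 | abs(t) ≥ 2.50 |

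A p-value of .05 or less needs |t| ≥ 2.01. BF01 ≥ 3 and p ≤ .05 therefore cannot occur together.

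**Step 2: how often the result is uninformative.** The BF01 ≥ 3 region lies wholly inside p > .05, so

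P(p > .05 and BF01 < 3) = P(p > .05) − P(BF01 ≥ 3).

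P(p > .05) is 0.950 at d = 0. At d = 0.5 it is 1 − 0.438 = 0.562.

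| r | True d | P(p > .05) | P(BF01 ≥ 3) | Difference |
|---|---|---|---|---|
| 0.5 | 0 | 0.950 | 0 | 0.950 |
| 0.5 | 0.5 | 0.562 | 0 | 0.562 |
| 0.707 | 0 | 0.950 | 0.505 | 0.445 |
| 0.707 | 0.5 | 0.562 | 0.119 | 0.443 |
| 1.0 | 0 | 0.950 | 0.700 | 0.250 |
| 1.0 | 0.5 | 0.562 | 0.212 | 0.350 |

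A simulation of 200,000 trials at r = 0.707 agrees: P(BF01 ≥ 3) was 0.506 at d = 0 and 0.119 at d = 0.5.

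**Step 3: what each result tells the reader.** The ratio of the probability under no effect to that under 0.5 SD, for p > .05 with BF01 < 3, is 0.950/0.562 = 1.7 at r = 0.5, 0.445/0.443 = 1.0 at r = 0.707 and 0.250/0.350 = 0.7 at r = 1.0. That result barely moves the odds. For BF01 ≥ 3 the ratio is 0.505/0.119 = 4.2 at r = 0.707 and 0.700/0.212 = 3.3 at r = 1.0. The distinction that the plan leaves out is the informative one.

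**The case against.** The strongest reply is that the wording is loose but harmless. The subscript in BF10 or BF01 shows which hypothesis the number favours. The two Recommended elements entries say only that 3 or more is significant, which fits an evidence threshold for either hypothesis. On that reading p > .05 with BF01 ≥ 3 is already concordant, and values from 1 to 3 already fall below the bar. This may well be what was intended. But the plan does not say so, Inference criteria ties the threshold to effects, and the equivalence sentence lets a non-significant test stand as equivalence regardless of the Bayes factor.

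A reader might infer that the rule will declare false effects. The documents do not support that. If the Inference criteria sentence requires both conditions, BF01 ≥ 3 with p ≤ .05 is impossible at this size; if the conditions are separate, the p-value governs.

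A reader might also infer that the threshold is met more often with no effect than with a real one. Taken literally at r = 0.707, it is met in 52.3% of trials at d = 0 and 40.3% at d = 0.5, but in 70.3% at d = 0.8. The reversal holds only below about 0.64 SD (about 0.82 SD at r = 1.0) and never at r = 0.5. The plan fixes neither prior nor effect size, and these rates are not error rates of any decision it makes.

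Finally, the figures are for an unadjusted two-group contrast. They match the planned CSQ-8 and BTPS t-tests, but only approximate the covariate-adjusted comparison to which the equivalence sentence refers. Bayes factors for the full mixed-model ANOVAs were not computed. That limit stands.

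**Conclusion.** The point holds as a defect in how null results are interpreted, not as a threat to type I error. The Bayes criterion has no direction, BF01 has no stated role, and no result is called inconclusive, in a plan that reads a null comparison as equivalence.

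With 27 per arm and a prior scale of 0.707, about 44% of trials with a true 0.5 SD difference would give p > .05 with BF01 below 3 and could be read as equivalent. The figure is about 56% at scale 0.5 and 35% at scale 1.0. The size depends on the assumed prior and effect; the need for a stated rule does not. The prior also decides whether evidence for no effect is attainable at all, since the largest possible BF01 is 2.79 at scale 0.5.

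The correction has a limit. At scale 0.707, about 12% of trials with a true 0.5 SD difference would still give BF01 ≥ 3. Nor does a directed BF01 supply the margin that a non-inferiority claim needs.

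**What to change.** In Inference criteria and in both Recommended elements lists, replace the Bayes factor sentence with a directional rule:

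- BF10 ≥ 3 is evidence for an effect; BF01 ≥ 3 is evidence for no effect; anything else is an inconclusive Bayes result.
- p > .05 with BF01 ≥ 3 is concordant, not discrepant.
- p > .05 with BF01 < 3 is reported as inconclusive, not as no difference.

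Amend the equivalence sentence in items 1 and 10 of Recommended elements to match, so that a non-significant test alone no longer counts as equivalence. State the prior and its scale before the data are analysed.

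The cost is a few sentences, with no new data or analyses. The downside is that some null results will be labelled inconclusive: with no true effect, about 44% of trials at scale 0.707, 25% at scale 1.0, and every non-significant result at scale 0.5.

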## Data exclusion

*How will you determine which data points or samples (if any) to exclude from your analyses? How will outliers be handled?*

Outliers (3 SD or more beyond group mean) will be windsorized relative to the group mean. Group = BPT or CET.

Attrition: If available, mid-treatment data will be substituted for missing post-treatment data. If not available, the most proximal (non-pre-treatment) data point for that child will be substituted. If not available, single imputation will be used based on all available demographic and performance data.

Duplicate Data: In cases of duplicate data with different administration dates, the first administration will be used unless there is compelling reason to select differently. If a child has duplicate task data from the same date, the file will be checked for notes (e.g., first administration was invalidated by fire alarm/child had to go to the bathroom). The first administration will be used unless there is a clear documented reason to select otherwise. If a participant has duplicate rating scale data from the same date (e.g., mom and dad filled out forms separately), we will select the rater who completed forms at the other time point. Priority will be given to ratings from the caregiver involved in treatment. Maternal ratings will be prioritized if no other distinguishing criteria are met. All decisions will be made without looking at the scores.

No checks will be performed to determine eligibility for inclusion in data analyses besides verification that each participant was consented and enrolled.

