#### Procedures

Pre-treatment testing occurred during a larger battery of two, 3-hour sessions. Post-testing occurred during a single, 3-hour session. A 90-minute mid-treatment testing session was conducted for children in the BPT group. As specified in the NIH R34 proposal, no mid-treatment sessions were completed for the first CET groups. This design difference was considered acceptable because it favored the null (i.e., test-retest effects, if present, would favor the BPT group). Statistical tests will therefore assess pre-post changes.

All tests were counterbalanced within/across sessions to minimize order/fatigue effects. Children received brief breaks after each task, and preset longer breaks every 2-3 tasks to minimize fatigue.

no file selected

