##### Central Executive Training (CET)

CET is a translational, evidence-informed, hybrid (in-office and at-home), software-based treatment protocol that includes gaming elements and an automated token economy to reinforce training goals and improve player engagement. The final 10-week protocol includes weekly, in-office sessions with the child (1 hour) and a concurrent parent psychoeducational group, combined with parent-supervised, in-home training (goal: 15-min/day, 2-3 days/week).

CET beta testing. The CET sample was recruited in 3 waves to facilitate software refinements and testing of key design features. As specified in the NIH grant proposal (R34 MH102499), the first subgroup trained on one game per week, the second subgroup had immediate access to all 9 training games, and the third subgroup (approximate n=9 per subgroup) received the final protocol that implemented all CET features. To reduce child expectancies, children were told that they were "beta testers" for our video game design team. Breadth of training across the 9 games was facilitated by a software algorithm that limited initial access each day to three games the child had not completed recently (third

subgroup only). Children earned additional rewards and access to all nine games for completing this daily "Mission Mode." Leveling was set to ensure incremental increases in difficulty based on child performance. This process occurred during the current study and involved iterative changes and extensive testing with graduate/undergraduate Research Assistants (alpha testing) and children with ADHD (beta testing).

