CET focus groups. Caregivers in the first two CET subgroups participated in focus groups. Key CET design changes based on these focus groups included overhauling the on-screen instructions, modifying the home screen to show child progress (daily games completed), and automation of the token economy via children earning on-screen 'tickets' that are exchanged for tangible, in-office rewards. Key logistical changes from these focus groups included improved communication with caregivers (e.g., access/login instructions, progress monitoring of days/games completed at home), modified expectations for at-home training duration (original goal of 30-minutes/day decreased to 15-minutes/day) and frequency (original daily training goal decreased to 2-3 days/week), and modified treatment duration (original 12-weeks decreased to 10-weeks). Finally, caregiver feedback resulted in the addition of a caregiver psychoeducational group that began mid-way through testing with subgroup 2. Most caregivers described homework as the biggest obstacle to at-home CET training; opinions were split approximately evenly regarding priority of CET vs. homework, with differences focused primarily on weighing immediate vs. delayed consequences.

no file selected

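### The attrition rule can fill missing post-treatment scores differently in the two arms and states no adjustment for doing so, so group x time can be biased in either direction and, if imputation is within arm, its standard error is too small

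*Combined protocol and SAP*

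**What the plan says.** The attrition paragraph under Data exclusion sets an ordered rule for both arms. First, "If available, mid-treatment data will be substituted for missing post-treatment data". If there is no such score, "the most proximal (non-pre-treatment) data point for that child will be substituted". If there is none of that kind either, "single imputation will be used based on all available demographic and performance data". The Missing data section plans to examine whether missingness at random is reasonable, but the same steps follow whatever that examination shows.

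The completed scores enter the mixed-model ANOVA or ANCOVA described under Covariates and Data Handling, with group x time as the critical test. Neither there nor in the outcome-specific sections is there a variance correction, an imputation model, a statement on whether treatment group is in that model, or a sensitivity analysis.

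On mid-treatment testing, the Procedures section says: "A 90-minute mid-treatment testing session was conducted for children in the BPT group". For the other arm it says "no mid-treatment sessions were completed for the first CET groups". It defends the difference as follows: "This design difference was considered acceptable because it favored the null". The reason it gives is that any test-retest effect would help BPT.

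**The concern.** A mid-treatment score put in place of a post-treatment score holds that child's gain at its mid-course level. An imputed score gives the child whatever gain the imputation model predicts. If missing BPT children mostly receive the first and missing CET children mostly the second, the group x time contrast picks up a difference made by the fill-in rule.

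The defence in Procedures does not reach this. It concerns practice effects from an extra testing session, whereas the fill-in rule is a separate mechanism and can move the contrast toward CET. That would matter most for parent-rated ADHD symptoms. There the plan expects both arms to improve, its research question is whether CET is non-inferior, and its Recommended elements read no difference as equivalence. An understated BPT gain would help the CET claim, but only if those scales were taken at mid-treatment, which the plan does not say.

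A second issue is precision. Single imputed values analysed as if they had been measured can make the reported standard error too small.

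**Working it through.** The plan gives no power calculation, effect size or attrition rate, so it has no figure of its own to reproduce.

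**Inputs from the plan.** 27 children per arm (Sample size); test-retest correlation .76-.90, used as a stand-in for the pre/mid/post correlation (Primary Outcomes, Working Memory); significance at .05 (Inference criteria).

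**Assumptions, not in the plan.** k = 3, 5 or 7 missing per arm, at random; half of any gain reached by mid-treatment; every missing BPT child has a mid score; no CET child has one; dropouts would have gained as completers do. The gain is 0.6 SD where an arm improves, with SD that of a single score. CET mid coverage is itself unknown. The subgroups are described as "approximate n=9 per subgroup". If only the first lacked mid sessions, up to about 27 - 9 = 18 CET children could have had one.

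**Bias, within-arm imputation.** Bias toward CET = (mB × uB - mC × uC)/27, where m is the number of children given a mid score and u is the gain still to come after mid-treatment. If both arms gain 0.6 SD, u = 0.3, mB = k and mC = 0:
- k = 3: 3 × 0.3/27 = +.033
- k = 5: 5 × 0.3/27 = +.056
- k = 7: 7 × 0.3/27 = +.078

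Simulation gave +.029 to +.033 / +.052 to +.059 / +.076 to +.080. If 2 / 3 / 5 of the missing CET children also have mid scores, the formula falls to (1, 2, 2) × 0.3/27 = +.01 / +.02 / +.02.

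**Bias, group omitted from the imputation, only CET gains.** Missing CET children receive the average gain of the pooled sample.
- Pool of observed post scores only: the average gain is 0.3, so the bias is -0.3k/27 = -.033 / -.056 / -.078.
- Pool that also contains the BPT children filled with mid scores: BPT makes up 27/(54 - k) of it, so the bias is -(k/27) × 0.6 × 27/(54 - k) = -0.6k/(54 - k) = -.035 / -.061 / -.089.

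Together these give about -.03 to -.04 / -.05 to -.06 / -.08 to -.09 SD.

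**Type I error when neither arm changes.** With d = k/27 imputed within arm in CET only, and ignoring the small part of change that the pre score predicts, the true variance is proportional to 1 + 1/(1 - d) and the reported variance to 1 + (1 - d). Their ratio is 1 - d, so reported SE / true SE is about √(1 - d) and type I error is about 2 × (1 - Φ(1.96√(1 - d))):

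| k | √(1 - d) | Approximate type I error | Simulated, within arm | Simulated, group omitted |
|---|---|---|---|---|
| 3 | .943 | 6.5% | 6-7% | about 5% |
| 5 | .903 | 7.7% | 6-8% | about 5% |
| 7 | .861 | 9.2% | 8-10% | about 5% |

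The simulations cover correlations of .76 and .90, with and without a residual draw.

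**Dropout related to the mid score.** At a correlation of .76 with no change in either arm, the bias is +.023 / +.034 / +.042 SD if low-scoring BPT children leave and -.021 / -.036 / -.042 SD if high-scoring ones leave.

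**The case against.** The strongest reply is that the harm may be slight. No attrition rate is given. Families who were offered treatment but did not take part form a separate untreated sample under Covariates and Data Handling, so few post scores may be missing. At 3 of 27 per arm, the bias is about .03 SD and type I error at most about 7%. On working memory the plan expects BPT not to change, so mid-treatment substitution adds little there. All of this stands and limits the size of the point.

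The reply can also be made on the imputation model. The plan imputes from demographic and performance data, and treatment group is neither. On that reading type I error stays near 5%. A reader might infer that the plan's test is inflated in every case; the documents do not support that, because the plan never says imputation is within arm. Omitting group does not rescue the rule, however: the primary contrast is then biased against CET if dropouts would have gained as completers do.

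Finally, imputation by arm has its own assumption. If gain stops at dropout and only CET gains 0.6 SD, the by-arm imputed mean is too high by about k × 0.3/27 = .033 / .056 / .078 SD toward CET (simulation: about +.04 / +.06 / +.08). In that case imputation that omits group is nearly unbiased (-.000 / -.005 / -.009). This stands, and it is why the fix includes a sensitivity analysis.

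**Conclusion.** The concern holds in conditional form. The plan states a concrete rule that can treat the arms differently, its stated reason for accepting unequal mid-treatment testing does not cover that rule, and no adjustment follows. Under the assumptions listed, and with up to 7 of 27 missing per arm, the bias can reach about .08 SD toward CET or .09 SD against it. Type I error can reach about 10% if imputation is within arm. These are illustrations and not bounds.

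Three stronger readings are not supported:
- **The rule favours CET.** The sign depends on which arm is still gaining after mid-treatment, whether group is in the imputation, which CET children had mid scores, and whether low or high scorers leave.
- **The bias vanishes only in one narrow case, such as a flat BPT arm with within-arm imputation.** It also cancels when the arms have equal substitutions and equal remaining gain. Within-arm imputation further requires that missing CET children gain as completers do.
- **The parent-rated outcomes are certainly affected.** Mid-treatment substitution reaches them only if those scales were completed at mid-treatment.

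**What to change.** Replace the attrition steps under Data exclusion with multiple imputation by arm, using pooled standard errors for the group x time contrast and its post-hocs.
- Impute the two tasks or subscales of an outcome together, from the pre scores and any covariates that the baseline comparison brings into the ANCOVA.
- Use mid scores as predictors only in an arm where every subgroup was measured on that outcome at mid-treatment.
- Delete the step that takes the nearest non-baseline score. No post-baseline testing other than mid and post is described for these outcomes.
- State whether winsorizing comes before imputation.
- Add a prespecified sensitivity analysis with reduced or no further gain after dropout.
- Keep mid-treatment substitution, and an observed-pairs analysis that also serves the Bayes factors, as labelled sensitivity analyses.
- State which measures were taken at mid-treatment and in which CET groups.

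The cost is plan wording and a multiple-imputation routine, possibly outside JASP; no new data are needed. In simulation, reported standard errors rose by 8-12% / 15-22% / 23-33% with 3 / 5 / 7 missing per arm. Of that, 5-8 / 9-11 / 12-17 points correct the understatement under within-arm single imputation. The rest is lost information and some conservatism of the method.
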